#### **Estimated Time to Target Accrual and Accrual Rate:**

**Study Sample Recruitment.** We will recruit 160 WLWH in total for this study. The sample recruited will be comprised of both **urban and rural Tanzanian WLWH**, **purposively stratified by age (18-24/25+)**. Eligible participants will be individually randomized in 8 waves (8 waves x 10 participants/wave x 2 sites (urban site and rural site) yielding the sample of 160 participants (80 intervention arm and 80 control arm).

We will recruit at community-based clinics, health centers, and dispensaries in the Kinondoni Municipal District (part of urban Dar es Salaam) and a rural area different from a previous R21 study (recruited rural participants from Lushoto); for this proposed study, we will recruit from one or more of the following rural sites – Bagamoyo, Kigamboni, Mkuranga. At both the urban and rural sites, staff at these organizations who are already aware of the woman's HIV status will approach potential respondents to introduce the study. At health centers and dispensaries, staff will be particularly encouraged to refer WLWH who are not regularly engaged in care and/or not virologically suppressed to help facilitate reaching a population not stably engaged and retained in care.

Study staff will only meet WLWH who, after learning about the study from the above agencies, indicate they are potentially interested in learning more the study. Convenience sampling will be employed, however purposively ensuring both young women (18-24) and older women (25+) living with HIV and urban and rural WLWH will be a focus. This study team has successfully recruited from these sites in previous studies.

## Time/Accrual Rate.

In accordance with the study timeline, we will recruit participants beginning in Year1/Month 6 and follow participants through Year 2/Month 9. Control and intervention eligible participants will be individually randomized in 8 waves (8 waves x 10 participants/wave x 2 sites (urban site and rural site) yielding the sample of 160 participants (80 intervention arm and 80 control arm). We estimate that it will take 6 months to complete recruitment.

#### **Data & Safety Monitoring**

• Summarize safety concerns, and describe the methods to monitor research subjects and their data to ensure their safety, including who will monitor the data, and the frequency of such monitoring. If a data monitoring committee will be used, describe its operation, including stopping rules and frequency of review, and if it is independent of the sponsor (per 45 CFR 46.111(a) (6)).

The MPIs ([name], [name], [name]) will virtually meet bi-weekly with the Project Leadership Team (please refer to study team structure) to monitor the conduct of the study and ensure that the study protocol is implemented as written. All project team members will be instructed to notify either the Tanzanian MPI ([name]) or contact MPI ([name]) if there is any adverse event. Once an adverse event is identified and/or reported, actual or potential, the MPI Steering Committee will virtually meet within 24 hours. The MPI Steering Committee will implement the appropriate course of action to remedy critical incidents and adverse events that may occur during the study. The MPI Steering Committee and the CRC, PD, Chief Statistician will conduct a data and safety review at mid-point of data collection and at any time a serious adverse event occurs.

During the study, if an adverse event were to be occur, the MPI Leadership Team, the CRC, and the Project Director will evaluate the adverse event and determine whether the event affects the risk/benefit ratio of the study and whether modifications to the protocol or consent form are required. A "Critical Incident Journal" will also be maintained during the project. This journal will contain information such as the nature of the critical incident, the personnel involved, the solutions considered, and the final action implemented to resolve the incident. When necessary, the study team will also seek the expert opinion of the Duke University Health System IRB, the Research Triangle International IRB, and/or the Muhimbili University of Health and Applied Sciences IRB. Safety concerns for participants in this protocol are minimal. However, non-serious adverse events will be summarized and reported to the IRB periodically. The summary will include the number of participants enrolled and a summary of graded adverse events to date. Should serious adverse events occur, they will be reported within 48 hours to the appropriate IRB as well as the NIH by the contact MPI ([name]).

All members of the investigative team have completed or will complete during the orientation/on-boarding process, in a standard program on the ethical conduct of human research that conforms to current NIH guidelines or the country-specific equivalent. This program included information on the history of human participant protection, ethical principles governing informed consent, risk/benefit evaluation, equitable selection of research participants, and regulatory oversight. The study protocol will be implemented by project staff that will receive standardized and verified training in study protocols and procedures and will be monitored in continued use of those protocols/procedures over the course of the study. A project database will be constructed using participant study numbers. A separate file, cross-referencing participant identification with project ID numbers, will be maintained with access limited only to staff working directly with the participants. Participants will be assured that they can withdraw from the study at any time without adverse effects. The Tanzanian MPI will be responsible for on-going quality control of the project database. The Tanzanian MPI, in collaboration with the other members of the MPI Leadership Team and Tanzanian Project Director, will ensure the confidentiality of all data and the results of monitoring, and will assist NIH by commenting on any problems that arise around the conduct of the study, participant enrollment, and data collection.

Regarding quantitative data integrity, field data collected by participants will be uploaded to a central database housed at TRI via an encrypted, secured network stored on servers behind RTI's firewall. REDCap (Research Electronic Data Capture) is a secure, web-based application that is HIPAA compliant and secure designed to support data capture. Data capture in the field, via REDCap, will use a tablet device with instruments preloaded in the local language (Swahili) and English.

During the quantitative data collection/analysis period, the key team members (MPIs, CRC, Project Director, Database Coordinator, Chief Statistician) will meet bi-weekly (every 2 weeks), and as needed, to discuss issues related to data elements/data analysis and results. The quantitative database used for storing data will be saved and backed up nightly on a secure encrypted server behind the firewall at RTI.

The MPIs, CRC, and PD will enact several safeguards to ensure that office and other space needed for the conduct of the proposed research to ensure the confidentiality of participants. Safeguards include the following:

a) all computers will be password-protected;

b) screensavers on computers will automatically initiate after 60 seconds of non-use;

c) all computers will be located in positions and angled so that casual observers cannot read computer screens;

d) all computers will contain the most current virus and security software and receive regular updates of this software;

e) all data collection materials will be stored in locked file cabinets inside a locked office, and access to these offices is limited to key study personnel (who have completed human participants' protection certification);

f) all data will be backed up nightly on a secure server and a flash drive will be used to store data off-site in the event of a building catastrophe; and

g) all data documents will be shredded or destroyed by the Tanzania MPI or PD at the appropriate time. We are confident that all research activities conducted for the study will protect the privacy and confidentiality of the study participants and will fully meet the requirements of human participants' protection.

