## **Standard Research Summary**

**Purpose of the Study** 

• Objectives & hypotheses to be tested

The scientific premise of this program of research is that stigma has significant and negative effects on various psychosocial, behavioral, and clinical outcomes associated with prevention, care, and treatment among Tanzanian WLWH.

For this specific study, we will obtain the following feasibility information:

• Recruitment metrics: length of time to complete participant recruitment; barriers to recruitment; percent of total participants screened who meet screening criteria (median score of IHSS; intention to remain resident in study area for duration of study) to meet sample size requirements for future RO1;

• Retention metrics: attendance and completion of the five group intervention sessions, punctuality. We will also monitor the number of pre-session contacts for each study participant and the amount and type of follow-up required for participants who miss one or more study visits.

 $\cdot$  Timing and Completeness of study instruments: time (minutes) it takes to complete the questionnaires; missing data from questionnaires.

• Fidelity: to evaluate fidelity to the study protocol and structured debriefing of each story, we will use detailed fidelity checklists. RAs will complete a process rating form at the end of each intervention session capturing issues of feasibility, coverage of debriefing session content, length of session, disruptions, issues raised during the session, and level of participant engagement with the material. The training team will maintain attendance rosters for each session, noting when participants leave the room and if/when they return.

Hypothesis: Although not formally articulated in the grant application, we hypothesis that the stigma intervention to be tested in this study (Labda Siku Moja) will reduce internalized stigma and improve coping self-efficacy, self-esteem, and hope among women living with HIV (WLWH) in Tanzania.

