**Intervention Procedures.** Before implementing the intervention, we will work with the Community and Technical Advisory Board (CTAB) to finalize all study procedures. The CTAB will consist of 6 to 8 individuals and will be co-chaired by a social/ behavioral scientist experienced in HIV research, [name], and a national HIV community advocate, [name], Program Coordinator and Co-Founder, Kimara Peer Educators and Health Promoters (please see letters of support). Other CTAB members may include health center or dispensary staff, a representative from TACAIDS and/or the National AIDS Control Program/ MOH, and at least one WLWH. This CTAB will provide guidance on all study and human subjects protection procedures and will help identify mechanisms to recruit WLWH who may be disconnected from care.

The intervention will be delivered via in-person groups. These groups will be held at either the dispensary or health center where the WLWH were recruited or at MUHAS. Regardless of site, the group/cohort meetings will occur in a private room. The stories of the *Labda Siku Moja* intervention will be viewed on either a health facility/dispensary TV or projected from a laptop using existing equipment. During the 5 weekly meetings, intervention arm participants will view one story and have a structured debrief by the Tanzania MPI; the structured debrief will use Motivational Interviewing (MI), a practical, empathetic, and short-term process that recognizes the difficulty of making life changes. MI utilizes a spirit of empathy, acceptance, respect, honesty, and caring, which helps in building warm, trusting relationships. MI will help the participants in the intervention arm of this study to explore and resolve issues, feelings, and insecurities associated with HIV-related stigma.

The recruited sample recruited will be comprised of both **urban and rural Tanzanian WLWH,purposivel y stratified by age (18-24/25+)**. Eligible participants will be individually randomized in 8 waves (8 waves x 10 participants/wave x 2 sites (urban site and rural site) yielding the sample of 160 participants (80 intervention arm and 80 control arm). Up to 200 may be consented to factor in for screen failures.

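### Adverse events have no scheduled question and no stated tabulation by arm, while intervention women have five extra contacts, so detection around the session period is unequal

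*Combined protocol and SAP*

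**What the plan says.** All references are to the combined protocol and SAP.

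- **Capture (Data & Safety Monitoring).** "All project team members will be instructed to notify either the Tanzanian MPI" or the contact MPI of any adverse event. No scheduled AE question, form or symptom list is described. Events are called graded, but no scale is named.
- **Periodic report (same section).** "non-serious adverse events will be summarized and reported to the IRB periodically", at an unstated interval. On content: "The summary will include the number of participants enrolled and a summary of graded adverse events to date". Arm is neither required nor excluded.
- **Other safety steps (same section).** "Once an adverse event is identified and/or reported, actual or potential, the MPI Steering Committee will virtually meet within 24 hours". For each event the leadership team, the CRC and the Project Director "determine whether the event affects the risk/benefit ratio of the study". Serious events are reported within 48 hours. The steering committee with the CRC, the Project Director and the Chief Statistician "will conduct a data and safety review at mid-point of data collection and at any time a serious adverse event occurs". A journal of critical incidents is kept.
- **Contacts in the intervention arm (Design & Procedures).** "During the 5 weekly meetings, intervention arm participants will view one story and have a structured debrief by the Tanzania MPI". Controls receive each site's routine care, and no study session is described for them.
- **Session paperwork (Purpose of the Study, Fidelity).** "RAs will complete a process rating form at the end of each intervention session capturing issues of feasibility", along with other items that include matters raised in the session.
- **Visits in both arms.** Design & Procedures gives baseline and days 30, 90 and 180. The Retention section lists follow-up visits at days 30, 60, 90 and 180.
- **Analysis (Data Analysis & Statistical Considerations).** There is no AE analysis.

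**The concern.** If an event is recorded only when a member of staff happens to learn of it, the chance of recording depends on how often staff see the woman. That frequency differs by arm by design. The extra contacts are also the ones most likely to bring distress to light: they are debriefs on HIV stigma, led by the Tanzanian MPI, who is one of the two people to whom AEs are to be notified. A session event thus has a short route into the record that controls lack.

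Two consequences follow. A total without arm cannot reveal an excess in one arm. And if the events as collected were later split by arm, part of any excess among intervention women could come from closer observation. The study is meant to inform a larger trial, whose planners will want to know how often participants were upset or harmed compared with usual care. Events that were never asked about at a visit cannot reliably be recovered afterwards.

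**Working it through.** **Inputs.** From the documents: 5 sessions; 3 common post-baseline visits (Design & Procedures) or 4 (Retention); 8 waves × 10 women × 2 sites = 160 women, 80 per arm. The plan gives no AE rate, detection probability or contact total, so it has no figure of its own to reproduce here. Assumed: a per-contact probability p that a current event is disclosed and recorded, from 0.05 to 0.30; equal true risk in both arms; events that persist once begun; full attendance.

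**1. Contacts.** 5 + 3 = 8 against 3 (ratio 2.67), or 5 + 4 = 9 against 4 (ratio 2.25). Pre-session contacts and the focus group add an unstated number.

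**2. Upper bound: every event precedes the first session and persists to day 180.** The chance of being recorded at least once over k contacts is 1 − (1 − p)^k.

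| p | 8 contacts | 3 contacts | Ratio | Ratio for 9 v 4 |
|---|---|---|---|---|
| 0.05 | 33.7% | 14.3% | 2.36 | 1.99 |
| 0.10 | 57.0% | 27.1% | 2.10 | 1.78 |
| 0.20 | 83.2% | 48.8% | 1.71 | 1.47 |
| 0.30 | 94.2% | 65.7% | 1.43 | 1.26 |

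**3. Onset spread evenly over days 0 to 180.** Only contacts after onset count. The documents give no session calendar, so sessions are assumed at days 7, 14, 21, 28 and 35, with visits at days 30, 90 and 180. Worked for p = 0.10:

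| Onset (days) | Length | Contacts left, intervention / control | Recorded, intervention / control |
|---|---|---|---|
| 0–7 | 7 | 8 / 3 | 0.570 / 0.271 |
| 7–14 | 7 | 7 / 3 | 0.522 / 0.271 |
| 14–21 | 7 | 6 / 3 | 0.469 / 0.271 |
| 21–28 | 7 | 5 / 3 | 0.410 / 0.271 |
| 28–30 | 2 | 4 / 3 | 0.344 / 0.271 |
| 30–35 | 5 | 3 / 2 | 0.271 / 0.190 |
| 35–90 | 55 | 2 / 2 | 0.190 / 0.190 |
| 90–180 | 90 | 1 / 1 | 0.100 / 0.100 |

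Weighting by length gives 35.28/180 = 0.196 against 28.53/180 = 0.159, a ratio of 1.24. At p = 0.05, 0.20 and 0.30 the same sum gives 1.29, 1.16 and 1.10. With sessions at days 0 to 28 the ratios run from 1.20 to 1.07.

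**4. Onset only within the assumed five-week session period (days 0 to 35).** The same calculation gives 1.89, 1.74, 1.51 and 1.34 for p = 0.05, 0.10, 0.20 and 0.30.

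**5. What a total without arm hides.** Suppose 12 women have an AE: 12/160 = 7.5%. That figure is the same for a 6/6 split (Fisher p = 1.00) and a 10/2 split (Fisher p = 0.032).

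**6. Why contacts are not a remedy as denominator.** Under step 2 at p = 0.10, recorded events per contact are 0.570/8 = 0.071 against 0.271/3 = 0.090. With no true difference, the intervention would look about 21% safer (0.071/0.090 = 0.79).

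**7. After equalising.** If only events elicited at the common visits are compared, k is 3 and 3 (or 4 and 4). The ratio is 1.00 at any p, provided p itself is the same in both arms.

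**The case against.** The other side has several good points.

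- **Silence is not a statement.** A reader might infer that AEs are to be pooled over arms and collected passively. The section says neither. It lists contents of the summary without excluding arm, and it is silent on the method of elicitation. What stands is that both are unspecified.
- **Harm could still be seen.** A reader might infer that the plan cannot show harm at all. That goes too far: each event prompts a meeting within 24 hours, serious events are reported separately, and the mid-point review includes the Chief Statistician and could be done by arm. These steps do not equalise detection, however, and no display by arm is promised for any of them.
- **The risk/benefit judgement does not rest on the summary.** A reader might infer that the team must weigh risk and benefit from a count without arm. The text asks for that judgement on each event, and the periodic summary is a separate report to the IRB. There is no contradiction here.
- **The larger ratios are an extreme case.** This is correct. Sessions span about five weeks, and an event that begins later meets the same contacts in both arms. The values of p are assumptions too.
- **The session form is not an AE form.** True: it is a process form. Its role as a detection route is an inference; the MPI's dual role is the firmer evidence.
- **No comparison of AEs by arm is planned, and risk is described as minimal.** Both are true, and they limit the weight of the point. They do not remove it, because the choice of how to ask must be made before the visits take place.

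**Conclusion.** The point holds as a cheap improvement. The plan's only stated capture route is staff notification, it describes no scheduled AE question, and it does not say that the summary is given by arm. Because intervention women have five extra sessions, AEs around the session period are more likely to be recorded in their arm, and a total without arm cannot show an excess in one arm.

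The direction rests on events being disclosed at study contacts. The size rests on assumptions that the documents do not supply: p between 0.05 and 0.30, equal true risk, persisting events and an assumed session calendar. On these, the apparent intervention-to-control ratio is about 1.3 to 1.1 with onset spread over 180 days, about 1.9 to 1.3 with onset confined to the session period, and at most 2.4 to 1.4 if every event precedes the first session. On the 9 v 4 schedule that upper bound falls to about 2.0 to 1.3.

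**What to change.** In Data & Safety Monitoring:

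1. Ask the same standard open AE question, in the same words, at every assessment visit common to both arms.
2. Tabulate those events by arm, with women randomised and women assessed as denominators. Do not use contacts.
3. List events that come to light in sessions separately, marked as intervention arm only, with no between-arm comparison.

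Reconcile the visit schedules in Design & Procedures and Retention, so that the set of common visits is settled.

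The cost is one question at existing visits and one changed table; no visits are added. The small downside is that recall at visits is less detailed than in sessions, which the separate list partly covers. A shared question does not remove any difference in readiness to disclose between women who have and have not attended sessions, so the table should be read with that in mind.
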